5.8 Duration of Therapy

In the absence of treatment delays due to adverse events, DMF will continue for 56 days as part of the clinical trial, or until:

- Disease progression
- Inter-current illness that prevents further administration of treatment
- Unacceptable adverse event(s)
- Patient decides to withdraw from the study, **OR**
- General or specific changes in the patient's condition render the patient unacceptable for further treatment in the judgment of the investigator.

Patients are not prohibited from continuing DMF through commercial source after the response assessment visit.

5.9 Duration of Follow Up

Patients will be followed for 1 year after removal from treatment or until disease progression, initiation of subsequent CLL therapy, or death, whichever occurs first. Patients removed from treatment for unacceptable adverse events will be followed until resolution or stabilization of the adverse event.

6.0 STUDY PROCEDURES

6.1 Schedule of Events

	Screening	Cycle 1 Day 1 (C1D1)	C1 D8	C2, D1	Up to 28 days after last DMF dose	56 days after last DMF dose	Follow-up (q 56 days until 1 year)
Visit Number	1	2	3	4	5	6	7-
Window	+/- 3 days		+/- 2 d	+/-7 d	+/-7 d	+/-7 d	+/-14 d
Informed Consent	X						
Serum Pregnancy test	X						
History and PE	X	X	X	X	X	X	X
Performance Status	X	X		X	X	X	X
Toxicity (include DLT) Evaluations		X	X	X	X	X	
Tumor Measurements by physical examination	X	X	X	X	X	X	X
CBC with differential	X	X (x2 – pre and post dose)		X	X	X	X
Comprehensive Metabolic Panel *	X	X (x2 – pre and post dose)	X	X	X	X	X
LDH, uric acid, phos		X (x2 – pre and post dose)					
Correlative laboratory collection **	X	X (x2 – pre and post dose)	X	X	X	X	
CT or MRI scan with contrast of chest, abdomen, pelvis					X		
Bone marrow biopsy and aspirate ***					X (if clinical response and imaging is consistent with CR)		

* Comprehensive metabolic panel (CMP) to include: albumin, alkaline phosphatase, ALT/SGPT, AST/SGOT, total bilirubin, electrolytes (sodium, potassium, calcium, chloride, bicarbonate), BUN, creatinine, glucose.

** Up to 30 mL in anti-coagulated (ACD) tubes for screening visit; up to 20 mL in anticoagulated (ACD) tubes for subsequent visits. To be drawn prior to DMF dosing.

*** With flow cytometric and immunohistochemical evaluation of CLL cell infiltrate; and chromosome and FISH analysis (including 11q, 12p, 13q, and 17p).

6.2 Screening/Baseline Procedures

Assessments performed exclusively to determine eligibility for this study will be done only after obtaining informed consent. Assessments performed for clinical indications (not exclusively to determine study eligibility) may be used for baseline values even if the studies were done before informed consent was obtained.

All screening procedures must be performed within 30 days prior to registration unless otherwise stated. The screening procedures include:

6.2.1 Informed Consent

6.2.2 Medical history

Complete medical, surgical and oncology history as well as history of infections are obtained at screening. Any changes from Screening (e.g. worsening severity or abnormal findings) are considered to be adverse events (AEs).

6.2.3 Demographics

Demographic profile will include date of birth, gender, race, and ethnicity.

6.2.4 Review subject eligibility criteria

Review of eligibility criteria as described in Section 3 to ensure subject qualification for study entry.

6.2.5 Review previous and concomitant medications

All prior medication taken by the subject within 4 weeks before starting the study is to be recorded. Concomitant medications taken by the subject during the study are to be recorded up until 28-days after last study dose. If a reportable adverse event (see Section 7) occurs within 28-days after last study dose, recording of concomitant medications should continue until resolution of the adverse event.

6.2.6 Physical exam including vital signs, height and weight

Vital signs (temperature, pulse, respirations, blood pressure), height, weight. (height is only required at screening.)

Physical exam including bidimensional measurement of palpable lymph nodes, spleen size (below the costal margin), and liver size (craniocaudal size at the right midclavicular line).

6.2.7 Performance status

Performance status evaluated prior to study entry, using ECOG grading scale.

6.2.8 Adverse event assessment

Baseline assessment of subject status for determining adverse events. See Section 9 for Adverse Event monitoring and reporting.

6.2.9 Hematology

Hematology to include hemoglobin (Hgb), platelets, total white blood cell count (WBC), and differential.

6.2.10 Serum chemistries

Comprehensive metabolic panel (CMP) to include: albumin, alkaline phosphatase, ALT/SGPT, AST/SGOT, total bilirubin, electrolytes (sodium, potassium, calcium, chloride, bicarbonate), BUN, creatinine, glucose, and LDH.

6.2.11 Blood draw for correlative studies

Up to 20 mL in anticoagulated tubes.

6.2.12 Pregnancy test (for females of child bearing potential)

Serum pregnancy test (in women of childbearing potential only, see definition in section 4.2); if serum pregnancy test has not been performed 14 days prior to dosing, a urine pregnancy test must be performed 7 days prior to dosing. If the test result is positive, patient dosing will be postponed until the patient's status is confirmed by a serum pregnancy test.

6.2.13 Tumor assessment

CT scan or MRI scan with contrast of thorax, abdomen, and pelvis. This may be done within 90 days prior to D1. Physical exam including bidimensional measurement of palpable lymph nodes, spleen size (below the costal margin), and liver size (craniocaudal size at the right midclavicular line).

6.3 Procedures During Treatment

6.3.1 Visit 2: Day 1

6.3.1.1 Review concomitant medications

6.3.1.2 Physical exam including vital signs (temperature, pulse, respirations, blood pressure), weight; and including bidimensional measurement of palpable lymph nodes, spleen size (below the costal margin), and liver size (craniocaudal size at the right midclavicular line).

6.3.1.3 Performance status using ECOG grading scale.

6.3.1.4 Adverse event assessment: See Section 9 for adverse Event monitoring and reporting.

6.3.1.5 Hematology: hemoglobin (Hgb), platelets, total white blood cell count (WBC), and differential.

6.3.1.6 Serum chemistries: Comprehensive metabolic panel (CMP) to include: albumin, alkaline phosphatase, ALT/SGPT, AST/SGOT, BUN, creatinine,

electrolytes (sodium, potassium, calcium, chloride, bicarbonate), glucose, and total bilirubin. Also: LDH, uric acid, phosphorous

6.3.1.7 Blood draw for correlative studies: Up to 20 mL in anti-coagulated (ACD) tubes.

6.3.1.8 Dispense DMF 120 mg PO BID x 7 day supply.

6.4.1.9 6-8 hours after DMF dosing: Repeat Hematology and serum chemistries, in addition to LDH, uric acid, and phosphorous. Blood draw for correlative studies: Up to 10 mL in anti-coagulated (ACD) tubes.

6.3.2 Visit 3: Day 8

6.3.2.1 Review concomitant medications

6.3.2.2 Physical exam including vital signs (temperature, pulse, respirations, blood pressure), weight; and including bidimensional measurement of palpable lymph nodes, spleen size (below the costal margin), and liver size (craniocaudal size at the right midclavicular line).

6.3.2.3 Performance status using ECOG grading scale.

6.3.2.4 Adverse event assessment: See Section 9 for adverse Event monitoring and reporting.

6.3.2.5 Hematology: hemoglobin (Hgb), platelets, total white blood cell count (WBC), and differential.

6.3.2.6 Serum chemistries: Comprehensive metabolic panel (CMP) to include: albumin, alkaline phosphatase, ALT/SGPT, AST/SGOT, BUN, creatinine, electrolytes (sodium, potassium, calcium, chloride, bicarbonate), glucose, and total bilirubin.

6.3.2.7 Blood draw for correlative studies: Up to 20 mL in anticoagulated tubes.

6.3.2.8 Dispense DMF at assigned dose x 21 day supply

6.3.3 Visits 4: Day 1 of cycles 2

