5.0 TREATMENT PLAN

5.1 Treatment Dosage and Administration

For Dose Level 1, DMF (Tecfidera formulation) will be administered at a dose of 120 mg PO BID (approximately 12 hours apart) for 2 x 28 day cycles.

For Dose Level 2, DMF will be administered at the currently used dose for patients with multiple sclerosis: 120 mg PO BID for 1 week, then escalate to the dose of 240mg PO BID for the remainder of 2 x 28 day cycles. The 1 week lead-in at 120 mg is to assist in toleration and initial side effects and is as per the standard prescribing information.

For Dose Level 3, DMF will be administered at the currently used dose for patients with multiple sclerosis: 120 mg PO BID for 1 week, then escalate to the dose of 360mg PO BID for the remainder of 2 x 28 day cycles.

The medication can be taken with or without food. Capsules should not be crushed or chewed. Capsules will be self-administered on an outpatient basis. On days in which patients are scheduled for assessment, capsules will be taken in clinic. Missed or vomited doses will be skipped. Patients are assessed for safety and tolerability on Day 8, Day 1 of each subsequent cycle, and 28 days and 56 days following the last dose of DMF.

Dose Level	DMF dose (all cohorts start at 120 mg PO BID dose for 1 week, then increase to the assigned dose)
1	120 mg PO BID
2	240 mg PO BID
3	360 mg PO BID

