5.2 Definition of Dose-Limiting Toxicity

Dose Limiting Toxicity (DLT) is defined as any of the following adverse events that are considered by the investigator to be possibly, probably or definitely related to DMF within the DLT evaluation timeframe.

- Non-hematologic adverse events: grade 3 (CTCAE 4) or higher, lasting more than 7 days despite appropriate medical management.
- Hematologic adverse events: grade 3 (iwCLL 2008) or higher, lasting more than 7 days despite appropriate medical management, with the exception of: any grade lymphopenia ; or any grade lymphocytosis.
- Grade 4 non-hematologic (CTCAE 4) of any duration
- Grade 4 hematologic (iwCLL 2008) of any duration.
- Any clinically significant toxicity that precludes administration of the next scheduled dose beyond 14 days

Replacement patients may be enrolled for patients who withdraw from investigational treatment for a reason that is definitely unrelated to toxicity of the study agent or disease progression (e.g. patient preference, loss to follow-up). Replacement patients will ensure enough patients are enrolled to evaluate the primary endpoint.

The DLT evaluation timeframe is from the first dose of DMF until day 56 of the trial.

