6.3.3.8 Dispense DMF at assigned dose x 28 day supply

6.3.4 Visit 5: Between 1 day and 28 days after cycle 2 day 28: Primary Endpoint Response Assessment

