8.1 Adverse Event Monitoring

Adverse event data collection and reporting, which are required as part of every clinical trial, are done to ensure the safety of subjects enrolled in the studies as well as those who will enroll in future studies using similar agents. Adverse events are reported in a routine manner at scheduled times during a trial. Additionally, certain adverse events must be reported in an expedited manner to allow for optimal monitoring of patient safety and care.

As far as possible, each adverse event should be evaluated to determine:

- duration (start and end dates)
- severity (grade)
- seriousness
- relationship to study agent
- action taken (i.e., none, study agent modification, medical intervention)
- outcome (i.e., resolved without sequelae, resolved with sequelae, ongoing)

Adverse events monitoring begins after initiation of study treatment and ends 28 days following the last administration of study treatment or study discontinuation/termination, whichever is earlier.

All patients experiencing an adverse event, regardless of its relationship to study drug (or at least possibly related to the drug), will be monitored until:

- the adverse event resolves or the symptoms or signs that constitute the adverse event return to baseline;
- any abnormal laboratory values have returned to baseline;
- there is a satisfactory explanation other than the study drug for the changes observed; or
- death.

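### The Day 1 and Visit 3 supplies have no spare days, so late but in-window visits can leave a fully adherent patient up to 7 days without DMF before Cycle 2 Day 1 (minor, cheap to fix)

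*Combined protocol and SAP*

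**What the plan says.** The protocol fixes three dispensing quantities:

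- Visit 2 (Day 1): "6.3.1.8 Dispense DMF 120 mg PO BID x 7 day supply"
- Visit 3 (Day 8): "6.3.2.8 Dispense DMF at assigned dose x 21 day supply"
- Visit 4 (C2D1): "6.3.3.8 Dispense DMF at assigned dose x 28 day supply"

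The window row of section 6.1 lets C1D8 move by 2 days and C2D1 by 7 days in either direction. No section mentions spare capsules, a scheduled interim refill, or what to do if supply runs out before a visit.

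Dosing is meant to be continuous. Section 5.1 sets, for Level 3, "120 mg PO BID for 1 week, then escalate to the dose of 360mg PO BID" for the rest of two 28-day cycles, and Level 2 has the same lead-in before 240 mg. Section 5.8 states: "In the absence of treatment delays due to adverse events, DMF will continue for 56 days". The safety window is tied to the calendar: "The DLT evaluation timeframe is from the first dose of DMF until day 56 of the trial" (section 5.2). The correlative footnote in section 6.1 says of the samples: "To be drawn prior to DMF dosing".

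**The concern.** The quantities fit a patient who attends on exactly the nominal days. A patient who attends late, but within the permitted window, runs out. No visit rule is broken and no dose is missed by the patient; the interruption comes from following the stated quantities and the stated windows together.

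Two things are affected. First, assigned-dose days are pushed past Day 56, so toxicity arising on them cannot count as a DLT. Section 10.3 would not pick this up, because DLT evaluability needs only 7 days of DMF plus completed safety follow-up. Second, at Levels 2-3 the C2D1 sample is the only correlative draw scheduled during dosing above 120 mg. The Day 8 sample precedes the step-up, and later samples follow the end of treatment. The C2D1 sample enters the on-treatment average that section 10.4 compares with the pre-treatment level, and it may be taken off drug.

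**Working it through.** **Inputs.** Supplies of 7, 21 and 28 days (6.3.1.8, 6.3.2.8, 6.3.3.8); C1D8 on Days 6-10 and C2D1, nominally Day 29, on Days 22-36 (6.1); lead-in of one week (5.1); DLT window Days 1-56 (5.2). Every dose is assumed taken and windows are counted from C1D1.

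**The plan's own figure.** 7 + 21 + 28 = 56 days, which matches section 5.8. The total is right; the lack of slack is the issue.

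**Drug-free days before C2D1.** Let V3 and V4 be the days of Visit 3 and C2D1.

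- Gap before Visit 3: A = max(0, V3 − 8).
- The first two supplies then last to the end of Day 28 + A.
- Gap before C2D1: B = max(0, V4 − 29 − A).
- Total: A + B = max(0, V3 − 8, V4 − 29).

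A late Visit 3 moves part of the gap earlier but does not add to the maximum, which is 36 − 29 = 7.

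**Consequences at Levels 2-3.** Assigned-dose days within Days 1-56 are 49 minus the total gap. If all dispensed drug is used, the last dosing day is 56 plus the total gap. The last column takes an evening dose on the last covered day and a morning draw.

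| Visit 3 | C2D1 | Days without DMF | Assigned-dose days in Days 1-56 | Last dosing day | Last dose to C2D1 draw |
|---|---|---|---|---|---|
| by Day 8 | Day 29 | 0 | 49 | 56 | about 0.5 day |
| by Day 8 | Day 30 | 1 (Day 29) | 48 | 57 | about 1.5 days |
| by Day 8 | Day 33 | 4 (Days 29-32) | 45 | 60 | about 4.5 days |
| by Day 8 | Day 36 | 7 (Days 29-35) | 42 | 63 | about 7.5 days |
| Day 10 | Day 31 | 2 (Days 8-9) | 47 | 58 | about 0.5 day |
| Day 10 | Day 36 | 7 (Days 8-9, 31-35) | 42 | 63 | about 5.5 days |

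Check of the fourth row: Days 8-28 give 21 and Days 36-56 give 21, so 42; 7/49 = 14% fewer. At Level 1, dosing days in the window fall from 56 to 49.

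**Sensitivity to how the C2D1 window is counted.**

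- Section 5.7 lists a Day 28 assessment. If C2D1 is read as Day 28, the latest visit is Day 35, the maximum gap is 35 − 29 = 6, and 49 − 6 = 43 assigned-dose days remain.
- If the window runs from the actual Visit 3, then V3 = 10 allows C2D1 up to 10 + 21 + 7 = Day 38. Days 8-9 and 31-37 are uncovered, 2 + 7 = 9 days, and 49 − 9 = 40 remain.

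**Check of the remedy.** With 9 days at Day 1 and 28 at Visit 3, the worst cases are covered: V3 = 8 covers Days 8-35 for C2D1 on Day 36, and V3 = 10 covers Days 10-37, enough for C2D1 on Day 36 or Day 38. Assigned-dose days become 49 (Visit 3 by Day 8), 48 (Day 9) or 47 (Day 10). Only 5 spare days at Visit 3 would not do: with V3 = 8, 26 days cover Days 8-33 and leave Days 34-35 without assigned-dose drug.

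**The case against.** The strongest reply is that a visit window moves an assessment and does not authorise stopping drug. Sections 5.1 and 5.8 require continuous dosing, nothing forbids an extra refill, and this is a single-center trial of a commercially available drug with its own investigational pharmacy. Bridging a few days would be ordinary practice. The full gap also needs C2D1 at the edge of its window and no leftover capsules, while section 5.1 has missed doses skipped, which leaves some over. Much of this stands: sites may well bridge, and the figures above are maxima. But the dispensing quantity is explicit, no bridging step is written, and a site that follows the text as it stands interrupts dosing.

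It is also fair that the protocol tolerates larger losses. Section 10.3 accepts 7 days of DMF for DLT evaluability, and section 5.7 allows delays of up to 14 days. This limits the weight of the point.

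A reader might infer more than the documents support:

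- **That treatment is lost.** All 56 days are still dispensed. No text says that days without supply are forfeited, though none says that they are made up.
- **That the dose decision is compromised.** The 21 assigned-dose days of cycle 1 stay inside the DLT window, section 9.1 places gastrointestinal events mainly in the first month, and no escalation rule changes. Toxicity on Days 57-63 is still recorded, since monitoring "ends 28 days following the last administration of study treatment" or at earlier study discontinuation, and section 10.4 runs to 56 days after completion.
- **That the marker analysis is diluted by a known amount.** Nothing in the documents allows that to be sized. Section 6.4 says not every assay is run at every time point, and draw and dose times (6.4.1) and the pill diary (9.1.2) already identify an off-drug sample. A Visit 5 on the first day of its window would also be close to a dose, although that timing is not required.

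**Conclusion.** The mismatch between supplies and windows is certain on the text; its weight is minor. The maximum is 7 days without DMF before C2D1 when windows are counted from C1D1, with a range of 6 to 9 because the plan does not state the anchor. With the 7-day gap at Levels 2-3, assigned-dose days within the DLT window fall from 49 to 42, and the C2D1 draw can come about 7.5 days after the last dose rather than about 0.5. These figures assume every dose is taken and no informal bridging. The documents give no frequency of late visits, so the expected effect cannot be stated. The case for change rests on the low cost, not on the size of harm.

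**What to change.** **Preferred.** In 6.3.1.8 dispense 9 days of 120 mg, and in 6.3.2.8 dispense 28 days at the assigned dose. State that dosing stops after 56 days, in line with section 5.8. Have surplus capsules returned or reconciled at C2D1 and again at Visit 5. Section 9.1.2 asks for returns only at the end of the study, so without this a punctual patient would hold surplus capsules alongside the cycle 2 supply. At Levels 2-3 the two extra Day 1 days avoid an interruption but only lengthen the lead-in.

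**Alternative.** In 6.1, allow Visit 3 no later than Day 8, and C2D1 no later than 21 days after the later of Day 8 and Visit 3. Together these make Day 29 the latest C2D1.

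**Cost.** Spare drug per patient is 2 days × 2 = 4 capsules of 120 mg at Day 1, then 7 days × 2 = 14 doses at Visit 3. That is 14 capsules at Levels 1-2 and 28 at Level 3 (one 240 mg plus one 120 mg per dose). Total supply becomes 9 + 28 + 28 = 65 days, against the 8 weeks that section 9.1 says the trial provides. The alternative costs slightly tighter scheduling. Either route needs an IRB-approved amendment (section 11.6), with no added visit or test.

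**Optional.** Add a sentence to section 10.4 that flags C2D1 samples taken off drug, using recorded dose times and an interval fixed before analysis, and reports them separately.

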6.3.3.1 Review concomitant medications

6.3.3.2 Physical exam including vital signs (temperature, pulse, respirations, blood pressure), weight; and including bidimensional measurement of palpable lymph nodes, spleen size (below the costal margin), and liver size (craniocaudal size at the right midclavicular line).

6.3.3.3 Performance status using ECOG grading scale.

6.3.3.4 Adverse event assessment: See Section 9 for adverse Event monitoring and reporting.

6.3.3.5 Hematology: hemoglobin (Hgb), platelets, total white blood cell count (WBC), and differential.

6.3.3.6 Serum chemistries: Comprehensive metabolic panel (CMP) to include: albumin, alkaline phosphatase, ALT/SGPT, AST/SGOT, BUN, creatinine, electrolytes (sodium, potassium, calcium, chloride, bicarbonate), glucose, and total bilirubin.

6.3.3.7 Blood draw for correlative studies: Up to 20 mL in anticoagulated tubes.

6.3.3.8 Dispense DMF at assigned dose x 28 day supply

6.3.4 Visit 5: Between 1 day and 28 days after cycle 2 day 28: Primary Endpoint Response Assessment

6.3.4.1 Review concomitant medications

6.3.4.2 Physical exam including vital signs (temperature, pulse, respirations, blood pressure), weight; and including bidimensional measurement of palpable lymph nodes, spleen size (below the costal margin), and liver size (craniocaudal size at the right mid-clavicular line).

6.3.4.3 Performance status using ECOG grading scale.

6.3.4.4 Adverse event assessment: See Section 9 for adverse Event monitoring and reporting.

6.3.4.5 Hematology: hemoglobin (Hgb), platelets, total white blood cell count (WBC), and differential.

6.3.4.6 Serum chemistries: Comprehensive metabolic panel (CMP) to include: albumin, alkaline phosphatase, ALT/SGPT, AST/SGOT, BUN, creatinine, electrolytes (sodium, potassium, calcium, chloride, bicarbonate), glucose, and total bilirubin.

6.3.4.7 Blood draw for correlative studies: Up to 20 mL in anticoagulated tubes.

6.3.4.8 Tumor assessment: Only if there are no lymph nodes that are 1.5 cm or larger by physical exam: CT scan or MRI scan with contrast of thorax, abdomen, and pelvis. This may be done within 7 days prior to or after Visit 10.

6.3.4.9 Only if clinical response and imaging are consistent with a complete response, subjects will have bone marrow aspirate and biopsy with samples sent for differential, morphology, and \geq 4-color flow cytometry for MRD. This may be done within 7 days prior, or 28 days following visit 10.

6.3.5 Visit 6: 56 days after the last dose of DMF

6.3.5.1 Review concomitant medications

6.3.5.2 Physical exam including vital signs (temperature, pulse, respirations, blood pressure), weight; and including bidimensional measurement of palpable lymph nodes, spleen size (below the costal margin), and liver size (craniocaudal size at the right midclavicular line).

6.3.5.3 Performance status using ECOG grading scale.

6.3.5.4 Adverse event assessment: See Section 9 for adverse Event monitoring and reporting.

6.3.5.5 Hematology: hemoglobin (Hgb), platelets, total white blood cell count (WBC), and differential.

6.3.5.6 Serum chemistries: Comprehensive metabolic panel (CMP) to include: albumin, alkaline phosphatase, ALT/SGPT, AST/SGOT, BUN, creatinine,

electrolytes (sodium, potassium, calcium, chloride, bicarbonate), glucose, and total bilirubin.

6.3.5.7 Blood draw for correlative studies: Up to 20 mL in anticoagulated tubes.

6.3.6 Visits 7-10: Every 56 days to one year (typically month 6, 8, 10, 12)

Patients will be followed every 56 days after completion of (or early withdrawal from) study treatment until subsequent CLL therapy, death, or discontinuation of trial participation. Follow-up will consist of survival contacts via medical record review, telephone call, or review of the Social Security Index.

